Cover page

Title: Mitigation of radiation pneumonitis and fibrosis

ClinicalTrials.gov Identifier: NCT01754909

Most recent IRB approval Nov 13, 2017

Protocol for “Mitigation of radiation pneumonitis and fibrosis”

Cohen VA 1531-01, CLIN-004-12S

Original from Oct 31, 2012 Registration packet, incorporating amendments through July 2015

Objective

This project will test the effect of enalapril, an angiotensin-converting-enzyme inhibitor, to mitigate radiation pneumonitis and fibrosis in veterans undergoing radiation therapy for lung cancer and other cancers in the chest. It is based on the hypothesis that human normal tissue radiation injury can be safely and effectively mitigated, and on our extensive studies of radiomitigation in experimental animals. Lung cancer is more common in veterans than in the general population; this project is highly relevant to the medical care of veterans.

Research design and methodology

Enalapril or placebo will commence after the start of irradiation in veterans undergoing radiation therapy for lung cancer and other cancers in the chest, and their effects on radiation pneumonitis and fibrosis will be compared as the primary outcome measure. Enalapril will be used rather than captopril, because enalapril is given in single daily doses. This is a prospective, double-blinded, randomized, placebo-controlled trial, in a secondary-tertiary care setting. Subjects will join this trial voluntarily, based on their planned radiotherapy for lung cancer, and it is planned to enroll 200 subjects over the five years of this study. The intervention of this study is the use of enalapril or placebo, which will be maintained for the lifetime of the study subject.

2. To test the mechanism of mitigation of radiation lung injury by enalapril.
 - a. Angiotensinogen, plasma renin activity, and angiotensin II will be measured as renin-angiotensin system markers in all subjects.
 - b. The effect of enalapril on each marker will be assessed, as compared to placebo.
3. To confirm that enalapril in this use does not adversely affect cancer treatment outcomes.
 - a. Cancer recurrence and death from cancer will be compared for the enalapril and placebo groups.

These studies will be done in men and women undergoing radiation therapy for lung cancer and other cancers in the chest. Enalapril, or identical-appearing placebo, will be started within a day

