Our retrospective clinical studies show that concurrent use of ACE inhibitors reduces the occurrence of radiation pneumonitis [and fibrosis], without lowering cancer-related survival. The safe mitigation of radiation injury has been identified as a priority by the National

Cancer Institute. We will address this critical problem. We hypothesize that the occurrence of radiation pneumonitis, fibrosis, or both in patients receiving radiation for lung cancer will be decreased by the ACE inhibitor enalapril, started after irradiation.

4. STUDY DESIGN. Provide a brief description of the design of the study (multicenter, double-blind, randomized, etc.) in narrative form. Do not provide details of specific procedures in this section (see Item 9 below). Include, as needed, a discussion of the appropriateness of research methods. Describe the statistical design and required sample size. Do not indicate "N/A" for this category.

This is a prospective, double-blinded, randomized, placebo-controlled trial, in a secondary-tertiary care setting. The ZVAMC and referring VAs in VISN 12 are the main centers; the Baltimore VAMC will be added. Subjects will join this trial voluntarily, based on their planned radiotherapy for lung cancer. We will enroll 200 subjects over the five years of this study. Statistical power analysis suggests the need for 200 subjects for the clinical endpoint, and ~ 100 subjects for the radiographic endpoint.

5. SUBJECT SELECTION AND EXCLUSION CRITERIA. Provide the specific criteria for including and excluding subjects in the study. Do not indicate "N/A" for this category.

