Men and women undergoing radiation therapy for lung cancer and other cancers in the chest at the Milwaukee VAMC and the Baltimore VAMC are eligible. Subjects will be recruited to this phase 2 trial after their diagnosis of cancer and after referral to Radiation Oncology for treatment. The existence of this study will be posted in the Radiation Oncology clinics. Subjects who require radiation therapy to attempt to cure or to palliate their disease will be eligible for this study. Subjects eligible for surgical resection and who do not need radiation therapy will not be eligible for this study. Subjects already on ACE inhibitors, angiotensin blockers, or renin antagonists will be excluded, but may participate if these medications are stopped by their treating physicians before the start of their participation in this study. Subjects with past history of allergy to ACE inhibitors will be excluded. Use of other antihypertensives is not an exclusion criterion. There will be no inclusion or exclusion by race or ethnic origin. Women and minorities are eligible. Children are not eligible because children do not develop lung cancer. Previous surgery and past or current use of chemotherapy are not exclusions. Subjects will have a Karnofsky performance status ≥ 70 , absolute neutrophils $> 1000/\text{mm}^3$, platelets $> 75,000/\text{mm}^3$, and hematocrit $> 25\%$. Liver and kidney function tests will be within normal range, alkaline phosphatase up to 1.2 and serum creatinine up to 1.1 times upper limit of normal, and baseline blood pressure will be systolic $> 110 \text{ mmHg}$ sitting. Pregnant or nursing subjects are excluded and fertile patients must have a negative pregnancy test and will use contraception. Lung function tests including spirometry, lung volumes and diffusing capacity will be obtained as part of standard of care for patients prior to radiotherapy, but indices from lung function tests will not be a cause for exclusion.

6. SUBJECT POPULATIONS. Indicate the subject populations to be recruited for the study.

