The study drug, enalapril or placebo, will be in addition to usual clinical care of subjects undergoing radiation therapy for lung cancer. Enalapril, or placebo, will be given orally, started within a day to up to 30 days of the beginning of the radiation treatments. They will be enrolled at the start of radiation therapy (RT), stratified for cancer stage, then randomized to enalapril or identical-appearing placebo. Randomization will be done by the Department of Biostatistics, Medical College of Wisconsin, using random number tables; the center pharmacies will be notified of the assignment to enalapril or placebo. There will be no stratification by age, gender, lung cancer histology, or use of chemotherapy since these do not have a consistent relation with the occurrence of RP. There is no stratification by center. Study drug is obtained from Expert Pharmacy Inc, with identical appearing enalapril and placebo tablets. It is held in the VA research pharmacy at Milwaukee, in a restricted access area under the aegis of the research pharmacist. It will be sent to patients at the Baltimore site upon their enrollment. The study drug dose will be

2.5 mg to start, and will be increased in increments of 2.5 mg to 10 mg per day, as tolerated. Clinical follow up of study subjects will be identical to that of subjects undergoing radiation therapy for lung cancer but who are not participating in this study, with the addition of four blood samples. One blood sample one week after starting the study will be to check for adverse effects of the study drug. Three more blood samples will be obtained for renin-angiotensin system (RAS) assays, done on three blood samples from each subject, at the start of the study, at 3 weeks after the start, and at the end of radiation therapy. Each of these four research-related blood samples will be approximately one teaspoon of blood obtained by venipuncture. Compliance is assessed by monitoring the requests for study drug refills. It will be verified at the end of the study by the elevation in plasma renin in subjects on enalapril compared to those on placebo. Study subjects will be monitored for adverse effects of study drug. The development, or not, of radiation pneumonitis and fibrosis will be assessed in the study subjects, as part of ongoing regular care, as are the periodic radiographic imaging and lung function testing. Quality of life will also be assessed.

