10. RISKS AND PRECAUTIONS. Provide a description of all risks (physical, psychological, social, legal, and/or economic) for each drug or procedure used. Indicate how risks will be minimized, including a description of procedures already being performed on the subjects for diagnostic or treatment purposes that will be used. Provide a description of these procedures. ***Distinguish risks associated with research from risks of therapies subjects would receive even if not participating in research.*** Include precautions to be taken to minimize the danger and/or pain. Provide a plan for notifying subjects of new findings that may affect their willingness to participate in the project. If there are no risks to participating in the study, this should be stated. Do not indicate "N/A" for this category.

Investigational devices: Include the risks of procedures involved in the use of investigational device and risks of investigational device compared to risks of alternative devices or procedures.

Enalapril is an angiotensin-converting-enzyme inhibitor in common use, for treatment of hypertension, kidney disease, and heart failure. It is used to lower blood pressure, and is also used in normotensive subjects with heart failure. Subjects with normal blood pressure who would use enalapril to mitigate radiation injury could develop low blood pressure which could cause dizziness and drug intolerance. This will be avoided by starting with low doses and increasing the drug dose, as tolerated. Elevation in serum potassium could occur; we will test for this in one extra blood sample, and monitor for it in subsequent usual clinical follow-up. Between 2 and 5% of subjects using enalapril could develop a cough, which resolves within a few days of stopping the drug. Intolerable cough will lead us to stop the study drug. The safety of enalapril in this use is very likely, because we have documented the safe use of lisinopril, another angiotensin-converting enzyme inhibitor and a congener of enalapril, in veterans at ZVAMC undergoing radiation therapy for lung cancer. These were subjects already on lisinopril when they underwent radiation therapy for lung cancer. We found no adverse effects of this use of lisinopril. In another study, we used captopril compared to placebo in bone marrow transplant patients, to mitigate chronic renal failure. There was no difference in drug tolerance in patients on captopril compared to those on placebo.

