The therapeutic risk is that of the medical care by, during, and after radiation therapy for

lung cancer. The research risk is that of the use of the study drug, enalapril or placebo, as detailed above. There is also the risk of obtaining blood for RAS studies. There is no alternative to the therapeutic risk, for subjects undergoing radiation therapy, because it is the standard of care for those subjects. The alternative to the research risk is to not participate in this study. The alternative is to undergo usual and customary care, by radiation therapy for the patient with lung cancer.

Data security and confidentiality will be maintained according to the rules of the Department of Veterans Affairs. Risks to breach of privacy and confidentiality will thereby be avoided. All data for this study will only be stored on password-protected VA computers. Data collection for complications of treatment, adverse and severe adverse events will be done by a dedicated study coordinator who will prospectively track all of the subjects of this study.

11. ANTICIPATED BENEFITS OF THE STUDY AND RISK/BENEFIT ASSESSMENT.

Describe the benefit to the subject and/or benefit to science. State if subjects will receive no benefit.

Investigational devices: Benefits of investigational device compared to benefits of alternative devices or procedures.

Subjects in this study may have a fifty percent or more reduction in the occurrence of radiation pneumonitis. Based on pre-clinical data in laboratory animals, we expect that to occur in subjects on enalapril compared to subjects on placebo. But this is not known or guaranteed, which is why this study of enalapril compared to placebo must be done. Based on extensive use of enalapril for other indications, and on our study of its congener, lisinopril, in veterans undergoing radiation therapy for lung cancer, the risks of this study related to use of study drug are small, and reasonable in relation to the anticipated benefits to subjects and others.

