e. The *frequency of data collection and assessments* of data or events captured by the monitoring plan, such as points in time or after a specific number of participants are enrolled.

f. The *definition of specific triggers or stopping rules* that will dictate when some action is required (e.g., studies may be stopped when there is a greater than expected rate of morbidity or mortality or when the experimental arm of a head to head comparison study is shown to be better or worse statistically than the standard care arm).

For retrospective studies, include whether or not you will discuss with the subjects potential study outcomes that may have an effect on their health or well being and when and how you will notify individual subjects or their health care providers of these findings.

Additional information is provided in “Data Safety Monitoring Plans” at the beginning of this packet

- a. *Data or events* to be captured included the development of adverse reaction s to study drug, including cough, low blood pressure, elevation in serum potassium, fall in white blood cell count, or red blood cell count (anemia). It is estimated that each of these have a risk of less than 5%. This information will be collected at study visits, upon report by study subject, will be documented on report forms, and will be verified by monthly chart reviews for all active subjects on this study. Serious adverse events (SAE) are those that cause significant morbidity or threat to life.
- b. Investigators and the study coordinator will *be responsible* for monitoring the data collected, and will report safety data to a central VA DMSB, the Data Monitoring Committee (DMC) at Hines VAMC, upon enrollment of 50, 100, 150 and 200 subjects.
- c. *DSMB reports* will be forwarded to the IRB at least yearly.
- d. Unanticipated problems involving risks to subjects or others (UAPs), internal serious adverse events (SAEs), and protocol deviations/violations will be reported to the IRB and the DMC using the local reporting form within 5 days of notification of the event.
- e. The *data collection will be continuous. The safety assessments* will be upon enrollment of 50, 100, 150, and 200 subjects.

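### In the supplied text, RAS blockers are restricted only at entry, so a treating physician may restart one on top of lifelong blinded enalapril or placebo

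*Protocol*

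**What the plan says.** **At entry.** Protocol section 5 excludes patients already taking an ACE inhibitor, an angiotensin blocker or a renin antagonist (together, RAS blockers). It reopens the door to them: they "may participate if these medications are stopped by their treating physicians before the start of their participation in this study". Other antihypertensives are allowed.

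**After entry.** The intervention is enalapril or placebo, "which will be maintained for the lifetime of the study subject" (Research design and methodology). Study drug "will be in addition to usual clinical care of subjects undergoing radiation therapy for lung cancer" (section 9).

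**Premise.** Section 3 states: "Our retrospective clinical studies show that concurrent use of ACE inhibitors reduces the occurrence of radiation pneumonitis".

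**Compliance and markers.** RAS blood samples are taken at the start, at 3 weeks and at the end of radiotherapy. Compliance is followed through refill requests and is to be "verified at the end of the study by the elevation in plasma renin in subjects on enalapril compared to those on placebo" (section 9).

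**Safety.** Section 10 names low blood pressure and raised potassium as risks. The dose is titrated as tolerated, one extra blood sample is taken at one week, and for potassium the plan is then to "monitor for it in subsequent usual clinical follow-up". Event data are collected by "a dedicated study coordinator who will prospectively track all of the subjects of this study". Under section 12, information on adverse reactions to study drug "will be verified by monthly chart reviews for all active subjects on this study", and the data monitoring committee sees safety data at 50, 100, 150 and 200 subjects.

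**The concern.** The trial knowingly admits patients who have just come off a RAS blocker and leaves them in usual care. A physician who sees blood pressure rise, or who withdrew the drug reluctantly, has a plain reason to restart it and no instruction from the trial. Two things are at stake.

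- **Safety, enalapril arm.** A restart adds a second RAS blocker to study enalapril while the physician is blind to it. Low blood pressure and high potassium are the protocol's own named risks, and both become more likely.
- **Interpretation, placebo arm.** By the protocol's premise, an ACE inhibitor taken around irradiation lowers RP. A placebo subject who starts one before RP develops receives the class under test, which shrinks the difference between arms. If it starts before the last RAS sample, it also blurs the marker comparison and the renin check on compliance.

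**Working it through.** **Step 1: look for a rule after randomisation.**

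| Place | What it covers | Rule on restarting a RAS blocker? | Record of it required? |
|---|---|---|---|
| Protocol 5 | Status before participation | No | No |
| Protocol 9 | Dosing, samples, refill requests | No | No |
| Protocol 10 | Risks, titration, potassium | No | No |
| Protocol 12 | Adverse reactions, chart review, committee | No | No; the review is described for adverse reactions |
| SAP | Power, endpoint, RAS and survival analyses | No | No allowance or handling |

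**Step 2: reproduce the SAP's sample size.** Inputs (SAP, Power analysis for aim 1): placebo RP pC = 0.11, effect 80%, so pE = 0.11 × 0.2 = 0.022; type 1 error 0.05; power 0.80. With p̄ = (0.11 + 0.022)/2 = 0.066:

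n per arm = [z_α √(2p̄(1−p̄)) + z_β √(pC(1−pC) + pE(1−pE))]² / (pC − pE)²

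One-sided: [1.645 × 0.3511 + 0.8416 × 0.3456]² / 0.088² = 97.4, against the SAP's 97. Two-sided, the formula gives 124. The SAP does not state sidedness, so both are carried below. That is a separate matter and adds no weight here.

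**Step 3: add restarts.** Let f be the share of placebo subjects who restart an ACE inhibitor before RP, and m the fraction of the full 80% effect they receive. Neither is in the documents; both are assumptions. Then:

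pC(f, m) = 0.11 × (1 − 0.8·m·f)

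For f = 0.10 and m = 1, pC = 0.11 × 0.92 = 0.1012. The difference falls from 8.8 to 0.1012 − 0.022 = 7.9 points.

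Power at n = 100 per arm (200 planned, equal arms) is Φ{[(pC − pE)√n − z_α √(2p̄(1−p̄))] / √(pC(1−pC) + pE(1−pE))}:

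- f = 0: Φ[(0.880 − 0.5776)/0.3456] = Φ(0.875) = 80.9%
- f = 0.10: Φ[(0.792 − 0.5593)/0.3354] = Φ(0.694) = 75.6%

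The SAP names chi-square or Fisher's exact test, so exact power was also computed by summing over both binomial distributions (chi-square uncorrected).

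| 11% vs 2.2%, 100 per arm | No restarts | f = 0.10, m = 1 | Loss, points |
|---|---|---|---|
| One-sided, formula | 80.9% | 75.6% | 5.3 |
| One-sided, chi-square | 85.6% | 80.5% | 5.1 |
| One-sided, Fisher | 74.4% | 66.8% | 7.6 |
| Two-sided, formula | 71.1% | 64.6% | 6.5 |
| Two-sided, chi-square | 74.3% | 66.9% | 7.4 |
| Two-sided, Fisher | 64.9% | 56.4% | 8.5 (8.4 before rounding) |

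**Step 4: vary the assumptions.**

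- Half the effect or half the share (m·f = 0.05, pC = 0.1056): power in the same row order is 78.4, 83.2, 70.7, 67.9, 70.8 and 60.8%, a loss of 2.4 to 4.1 points.
- Placebo RP 20%, effect 80% (20% vs 4%), one-sided, f = 0.10, m = 1: formula 97.1 to 94.8%, chi-square 98.1 to 96.3%, Fisher 96.8 to 94.0%, a loss of 1.8 to 2.8 points.
- For scale: at 11% RP and 70% efficacy with no restarts, the one-sided formula gives 68.2%. Uncertainty about efficacy matters more than restarts.

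**The case against.** **The file is incomplete.** The last part of the protocol, the consent form and the report forms were not available, and a medication rule or field could well sit there. This stands. A reader might infer that the trial has no such rule anywhere; the documents do not support that, and the point is limited to the supplied text.

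**The entry criterion implies abstinence during participation.** That is a fair guess at its purpose, but the wording sets a condition before the start and says nothing afterwards. A physician at either site could restart the drug without departing from the text.

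**A restart would be seen anyway.** Partly true: the coordinator follows every subject and charts are read monthly, so a prescription may come to light. It would be wrong to infer that restarts are invisible. But nothing requires that one be written down as trial data. The SAP's planned regression on patient factors can use it only if it is captured.

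**Harm is monitored.** Titration, the one-week sample, potassium follow-up, chart review and committee review are real safeguards. They can detect harm once the drugs overlap; none prevents the overlap.

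**The power loss is assumed.** This also stands. It is tempting to conclude that restarts leave the trial underpowered. The documents give no restart rate and no effect for a drug restarted later, so no such conclusion follows. Nor does lifelong treatment mean that every restart matters: only those before RP touch the primary contrast, and only those before the end of radiotherapy touch the RAS samples. The premise concerns ACE inhibitors; no RP effect is given for the other two classes.

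**Analysis set.** A reader might infer that subjects who restart would be dropped or moved between arms. The SAP merely does not say that RP is analysed by assigned arm, which is missing detail and not evidence of another plan.

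**Conclusion.** The point holds for the supplied text and is worth acting on. Followed as written, the plan permits blinded double RAS blockade in the enalapril arm and use of the tested class in the placebo arm, in a population that includes patients just taken off these drugs.

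The safety argument needs no restart rate. The effect on power is unknown. The illustration of about 5 to 8 points rests on 10% of placebo subjects restarting an ACE inhibitor before RP with the full 80% effect, at 11% versus 2.2% and 100 per arm. It shrinks to about 2 to 4 points at half the share or half the effect, and to 2 to 3 points one-sided at a 20% placebo rate. A rule would recover only the part due to avoidable restarts. Confidence is medium, because the unavailable text may already contain a rule.

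**What to change.** Add to Protocol section 9: *From randomisation, open-label ACE inhibitors, angiotensin blockers and renin antagonists are not given together with study drug. If blood-pressure treatment is needed, another class is used where the treating physician finds it suitable. If a RAS blocker is needed, study drug is stopped first and follow-up continues.*

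At the monthly chart review, record four items for any RAS blocker: drug, start date, stop date and reason. In the SAP, add that restarts are reported by arm.

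The cost is small: a few sentences, four fields in a review that already takes place, and one table row. Other antihypertensives are already permitted, so treatment is not withheld. The downside is that some subjects will stop blinded study drug, and needed restarts will still dilute the contrast. They will, however, be counted, and they will no longer overlap with study enalapril. If the unavailable text already holds such a rule, a cross-reference in section 9 is enough.

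### Scheduled DMC safety reviews depend on enrolment alone and stop at subject 200, although study drug is lifelong and DSMB reports are due at least yearly

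*Protocol*

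**What the plan says.** Protocol section 12 (Data safety monitoring) sets the timing in three places.

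- Item b: safety data go to the DMC "upon enrollment of 50, 100, 150 and 200 subjects".
- Item e: data collection is continuous, but the safety assessments "will be upon enrollment of 50, 100, 150, and 200 subjects".
- Item c: DSMB reports "will be forwarded to the IRB at least yearly", with no end date.

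Two further items bear on safety oversight. Under item a, adverse reactions are "verified by monthly chart reviews for all active subjects on this study". Under item d, unanticipated problems, internal serious adverse events and deviations "will be reported to the IRB and the DMC using the local reporting form within 5 days of notification of the event", with no enrolment limit. Item f stops the study for a rate of morbidity or mortality above expectation, or when one arm is statistically better or worse than the other.

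On duration, the protocol's Research design and methodology section says of accrual that "it is planned to enroll 200 subjects over the five years of this study", and describes the intervention as enalapril or placebo, "which will be maintained for the lifetime of the study subject".

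The SAP (Survival analysis for aim 3) mentions interim masked safety analyses under an O'Brien correction but gives no schedule for them.

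**The concern.** Every scheduled look is tied to a head count, and the last one falls when subject 200 enters. That subject then has essentially no exposure, and recent entrants have little. The outcomes behind aim 3 (recurrence and death from cancer) and the 6- or 12-month fibrosis endpoint in the SAP appear well after entry, so much of this evidence matures when no review is scheduled.

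The enrolment triggers also do not fit item c. Unless accrual is faster than planned, some 12-month periods contain no new review on which a yearly report could rest. Slower accrual makes this worse, and if accrual stops short of 200 the last review is never triggered.

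At stake is the part of item f that compares the arms. The trial sets out to confirm that enalapril does not harm cancer outcomes, yet after accrual the plan names no point at which a committee would look at the arms side by side while subjects remain on blinded drug.

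**Working it through.** The documents give no figure for exposure after the last review, so there is none to reproduce. What follows uses their inputs plus stated assumptions.

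**Review spacing.** 200 subjects over 5 years is 200/5 = 40 per year if accrual is even (assumption). Spacing is 50/40 = 1.25 years, so reviews fall at about months 15, 30, 45 and 60. Spacing of 12 months needs at least 50 per year. At half the planned rate (20 per year) the first review is at 50/20 = 2.5 years, month 30.

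**Follow-up at the last review, with no survival assumption.** At 40 per year, 40 subjects entered in the preceding 12 months and 80 of 200 in the preceding 24. Those 80 cannot yet have reached the SAP's two-year disease-free survival time point.

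**Share of drug exposure after the last review.** Inputs:

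- accrual of 200 subjects, even over A = 5 years (total and period from the protocol; evenness assumed);
- median survival m of 12, 18 or 21 months, from the SAP's survival power table, used as a stand-in for time on drug;
- exponential survival with yearly rate L = ln 2/(m/12), and drug until death (assumed).

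Formulas:

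- share after year 5 = (1 − exp(−LA))/(LA);
- alive at year 5 = 200 × share;
- total exposure = 200/L;
- remaining exposure = (alive at year 5)/L.

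At m = 18: L = 0.6931/1.5 = 0.4621 and LA = 2.310. The share is (1 − 0.0992)/2.310 = 0.390. About 78 subjects are alive at year 5. Total exposure is 200/0.4621 = 433 person-years, of which 78.0/0.4621 = 169 remain.

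If 20% per year also stop drug (an assumed rate; the documents give none), add −ln(0.8) = 0.2231 to L.

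| Scenario | L per year | LA | Share after last review |
|---|---|---|---|
| Median 12 months | 0.693 | 3.466 | 28% |
| Median 18 months | 0.462 | 2.310 | 39% |
| Median 21 months | 0.396 | 1.980 | 44% |
| Median 18, 20%/year stop | 0.685 | 3.426 | 28% |
| Median 12, 20%/year stop | 0.916 | 4.581 | 22% |

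**Finite follow-up, median 18 months.** Exposure before the last review is 433 − 169 = 264 person-years. Counting only c further years, the later exposure is 169 × (1 − exp(−0.4621c)).

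- c = 1: 62 person-years, and 62/(264 + 62) = 19%.
- c = 2: 102 person-years, and 102/(264 + 102) = 28%.
- c = 0 (exposure ends at year 5): 0%.

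**How long yearly review could run.** With 78 subjects on drug at year 5 and L = 0.4621, the expected number falls below one after ln(78)/0.4621 = 9.4 years.

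**The case against.** The strongest reply is that oversight does not end at subject 200. Item d sends serious events and unanticipated problems to the DMC within 5 days throughout, and item a has monthly chart reviews of active subjects. Item f is not tied to the enrolment reviews, and its morbidity-or-mortality limb needs no comparison of arms. All of this stands. A reader might infer that harm emerging after accrual could not stop the trial. The documents do not support that: the DMC could act on individual reports or call an unscheduled review. What remains is that no scheduled look is named for the between-arm limb.

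Second, item c has no end date and can be read as a calendar commitment that continues after accrual. So a reader who concludes that yearly reports are impossible goes too far, since item c does not say that each report needs a new enrolment-triggered review. But b and e both state enrolment counts only, so the three items still disagree on timing.

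Third, the exposure share is not a figure of the plan. The 18 months is cancer survival from a power table, not time on drug. Palliative patients are eligible ("Subjects who require radiation therapy to attempt to cure or to palliate their disease will be eligible for this study"), and section 10 foresees stopping drug for intolerable cough. Both would lower the share. If the study really closes at five years, the later exposure falls outside it altogether. This stands, and it is why only a range is given. It also exposes an unresolved point in the protocol itself: lifelong study drug beside a five-year study.

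**Conclusion.** The point holds as a conflict and a gap in scheduling. Items b and e give four enrolment-triggered reviews and nothing after subject 200. At planned accrual these are about 15 months apart, which does not match item c. After accrual, the between-arm part of item f has no scheduled look.

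The spacing depends only on even accrual at 40 per year. The exposure share depends on much more. It is 28% to 44% over the SAP's own medians with drug until death (39%, with about 78 of 200 subjects alive, at 18 months), 22% to 28% with 20% per year stopping drug at a 12- or 18-month median, and 0% if exposure ends at year 5. A reader might take about 40% as a property of the plan. It is one scenario near the upper end of that range and should not be quoted without its assumptions.

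This should be corrected. It does not show that safety is unmonitored, because reporting of individual events continues.

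**What to change.** Change items b and e so that a DMC review takes place at 50, 100, 150 and 200 enrolled or every 12 months, whichever comes first, and continues yearly after enrolment closes until study follow-up closes. Align the yearly reports in item c with these reviews. List the added looks in the SAP under its O'Brien correction. The protocol's lifelong study drug and five-year study must also be reconciled, and the documents should state how; that choice belongs to the sponsor.

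The data are already collected continuously, so the cost is wording and reports. If each review falls due at the next enrolment count or 12 months after the previous review, planned accrual gives reviews at months 12, 15, 27, 30, 42, 45, 57 and 60: eight instead of four, so four more. After enrolment closes there is one report per year of follow-up, or about nine if follow-up ran until the last subject is off drug (18-month median, no discontinuation). The statistical price is slightly more interim looks to account for.
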